8.2. Secondary Objectives

 To retrospectively assess the efficacy consequences of NA and OIA, after adjusting for baseline characteristics and other confounders, overall and by cohort, on the odds of becoming unsuppressed, in subjects with and without resistance development. The protocol definition of unsuppressed is: HIV RNA>50 copies/mL in two consecutive measures within regimen duration, occurring within the observation period; among patient-regimens with HIV RNA ≤50 copies/mL at the start of the regimen if the regimen started during the observation period, or at the start of the observation period if the regimen started before the observation period.

In order to evaluate the odds of becoming unsuppressed (with or without resistance development), laboratory / monitoring data shall be collected.

• To retrospectively assess the effect of NA and OIA on the odds of hospitalization, after adjusting for baseline characteristics and other confounders, overall and by cohort.

In order to answer this objective, hospitalization data of all patient-regimens included in the study shall be collected.

To retrospectively assess the impact of NA and OIA on mean monthly ART plus hospitalization costs (Gross Domestic Product [GDP] Purchasing Power [PP] converted current prices), after adjusting for baseline characteristics and other confounders, overall and by cohort.

Ideally, hospitalization and ART costs will be collected at the center level. If not possible, hospitalization costs will be collected from publicly available national lists of diagnosis-related groups (DRGs) and ART costs from IMS databases of each participating country.

To assess the impact of STR versus non-STR on:

- 1. becoming unsuppressed (defined as above)
- 2. being hospitalized
- 3. costs (ART plus hospitalization costs)

To retrospectively quantify ART prescription errors during the first 48 hours of hospitalization of HIV-1 adult patients, overall and according to the cohort. Prescription errors will be evaluated by reviewing all prescriptions made during the first 48 hours of every hospitalization episode included. Investigators shall review all medication orders during this period to identify ART prescription errors. Errors will be classified as

- 1. Absence / incomplete regimen when the regimen prescribed is incomplete (e.g. when the physician prescribes only one PI/r) or when the regimen is not prescribed although it should have been.
- incorrect dosage (including renal dose adjustment) when the dosage of a component/co-formulation of the regimen is not correct, i.e. the dosage prescribed does not exist
- 3. incorrect schedule when the schedule mentioned by the physician is not adequate to the regimen prescribed
- 4. incorrect formulation when the pharmaceutical form prescribed is not available
- 5. duplication of ART therapy
- 6. non-recommended drug-drug combinations (ART-ART and ART-non-ART), as suggested by Yehia et al. {27744, 22}. Non-recommended drug-drug combinations (between antiretroviral agents and/or antiretroviral agents and other drugs simultaneously) are available on the HIV Drug interaction website and are shown in red as contra-indicated:www.hiv-druginteractions.org/Interactions.aspx

9. **RESEARCH METHODS**

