Stady Design	patient adherence to ART. Adherence will be evaluated in a matched retrospective cohort study. Two cohorts will be considered: STR (defined as a regimen containing single tablet regimens presently recommended by the European AIDS Clinical Society (EACS) Version 7.0 October 2013 {27774} or Stribild) and non-STR (defined as a regimen containing multi-pill once daily combinations presently recommended by the European AIDS Clinical Society (EACS) Version 7.0 October 2013 {27774}. In order to maximize		
	homogeneity between the two cohorts and reduce the impact of treatment-selection bias we will be applying a propensity score		

	matching (PSM) approach. The statistical unit of analysis will be the patient-regimen. Data will be collected on patient-regimens that have been given for at least 90 days at any time between 1 st January 2009 and 31 st December 2013. This is the observation period.	
	All data introduced into the eCRF will be de-identified to maintain subject confidentiality. A study number will be assigned for each subject and patient-regimen.	
	Within the STR group, priority will be given to non-Atripla patient-regimens so these will be selected first if available.	
Sub-study design	A sub-study will review and quantify prescription errors. Only centers where prescription data is available will be included in the prescription errors sub-study. ART prescription errors will be evaluated by a retrospective review of medication orders during the first 48 hours of hospitalization (for any cause) for patients with HIV infection admitted to each participating center between 1 st January 2012 and 29 th December 2013. Each center participating in this sub-study will aim to include 40 hospitalization episodes. Prescription errors will be classified as:	
	1). absence / incomplete regimen	
	2). incorrect dosage (including renal dose adjustment)	
	3). incorrect schedule	
	4). incorrect formulation	
	5). duplication of ART therapy	
	6). non-recommended drug-drug combinations (ART-ART and ART-non-ART).	

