Neuner et al {27776} reported that medication errors with ART and opportunistic infections' drugs occur in 50% of admissions, with the majority of these errors (65%) not being recognized or resolved during the admission. In 2012, Yehia et al. {27744} found a total of 145 ART medication errors in 110 admissions on the first day (29%) and 22 errors in 21 admissions on the second day (7%). Pettit et al. {27768} also reported a significant association (p < 0.001) between medication errors and protease inhibitor drugs (PIs).

Most errors are caused by a lack of expertise with prescribing ART, failure to reconcile home or transfer medications, poor or no written or verbal communication between physicians, overlooking decision support software alerts and/or lack of ownership for HIV therapy when treating patients' primary problem {27744}. The correction of medication / prescription errors requires an intervention by the pharmacist and a discussion with the physician. In the Pettit et al. study, the majority of pharmacist interventions (68%) were related to dosage modification {27768}.

8. **RESEARCH QUESTIONS AND OBJECTIVES**

This study was designed to estimate the impact of each type of regimen (STR and non-STR) on adherence and prescription errors (sub-study) and to assess the impact of adherence on hospitalization and clinical and economic outcomes.

In order to do so, several research hypotheses were formulated:

- 1. that SA accounts for a non-negligible portion of OIA and that both SA and NA are clinically and economically relevant;
- 2. that STRs, as SA-free regimens, will improve adherence and generate clinical and economic benefits;
- 3. that STRs are, by nature, of value in avoiding prescription errors.

In this context, the aim of this international retrospective study is to evaluate the potential benefits of STR in enhancing adherence, and its clinical and economic consequences in the European context. The study also aims at quantifying prescription errors and identifying those that can be avoided by the use of STRs.

8.1. **Primary Objective**

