Odds of being hospitalized in STR versus non-STR groups, after adjusting for baseline characteristics and other confounders, using monitoring (hospitalization) data;

Odds of being hospitalized according to subject adherence level (NA and OIA), after adjusting for baseline characteristics and other confounders, using monitoring (hospitalization) data.

Costs

Average monthly ART plus hospitalization costs, adherence (OIA) adjusted, in each STR versus non-STR groups at GDP Purchasing Power Parity (PPP) converted current prices, after adjusting for baseline characteristics and other confounders;

Monthly ART plus hospitalization costs according to subject adherence level (NA and OIA), adherence (OIA) adjusted at GDP PPP converted current prices, after adjusting for baseline characteristics and other confounders.

Ideally, hospitalization and ART costs will be collected at the center level. If not possible, hospitalization costs will be collected from publicly available national lists of DRGs and ART costs from IMS databases of each country.

Prescription errors audit

Number of prescription errors in ART orders in the first 48 hours of hospitalization, overall and according to the cohort. Errors will be classified as:

- 1. absence / incomplete regimen
- 2. incorrect dosage
- 3. incorrect schedule
- 4. incorrect formulation
- 5. duplication of ART therapy
- 6. non-recommended drug-drug combinations (ART-ART and ART-non-ART), as suggested by Yehia et al {27744} and available on the HIV drug interaction website shown in red as contra-indicated; www.hiv-druginteractions.org/Interactions.aspx.

In order to collect this information, all prescriptions made during the first 48 hours of every hospitalization of all patient-regimens included shall be reviewed.

Taking into consideration the endpoints defined, the investigators believe that the study will answer the research questions.

Since this is a retrospective study that will only use data from subjects' clinical files and from prescription / laboratory and pharmacy files, treatment decisions will have already taken place, according to local treatment guidelines and/or routine clinical practice, and will not be influenced by the protocol.

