Inpatient care (all episodes performed in the observation period)	 For each episode: Date of admission Admission diagnosis Date of discharge Destination at discharge Event code (DRG) ICD-9 or ICD-10 code (primary and secondary) Total cost of hospitalisation, including medications
Antiretroviral treatment pharmacy refills (for each valid patient-regimen)	 For each drug of each regimen: Date of refill (dd/mm/yyyy) scientific / generic name (which includes active principles, dosages, pharmaceutical forms), Quantity dispensed
Adverse Drug Reactions	 For each episode Adverse Drug Reaction description Seriousness Start and End dates or ongoing Relation to Gilead drug
Pregnancy (if applicable)	 Last menstrual period Date of pregnancy confirmation Estimated date of delivery or outcome if available at the time of the review

Prescription errors sub-study

After confirmation of eligibility criteria, investigators will collect the following data for each hospitalization episode selected, based on clinical/pharmacy/prescription records:

Individual characteristics (at the beginning of each hospitalization enigode)	- Subject initials (where permissible)
	- Date of birth
episode)	- Gender (male, female, transgender)
	- Race (White, Asian, Black or African heritage, other)
	- Non ART concomitant medications
Inpatient care (for each hospitalization	- Date of admission
episode)	- Admission diagnosis
	- Date of discharge
	- Discharge diagnosis
	- Destination at discharge
	- ICD-9 or ICD-10 code (primary and secondary)
	- DRG code Admitting service: HIV/AIDS, Medicine, Surgery, Obstetrics and Gynaecology, Neurology / Psychiatry, Other
	- Degree of the prescribing physician: Assistant / Junior doctor, Graduated Assistant / Registrar, Senior Graduated Assistant / Consultant, Other
	- Transferred within the first 48 hours? If so where to and when?
	- ART prescribed in the first 48 hours: active substances, dosage of each, scheduling
Prescription errors audit (for each error)	- Type of error:
Prescription errors audit (for each error)	 Type of error: (1) absence / incomplete regimen
Prescription errors audit (for each error)	 Type of error: (1) absence / incomplete regimen (2) incorrect dosage [including renal dose adjustment]
Prescription errors audit (for each error)	 Type of error: (1) absence / incomplete regimen (2) incorrect dosage [including renal dose adjustment] (3) incorrect schedule

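### The only definition of dosage error in the prescription errors sub-study contradicts its own label: read literally, it leaves out existing but wrong doses and missed renal adjustment

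*Protocol*

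**What the plan says.** Error type 2 appears in four places in the protocol.

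- **Synopsis, sub-study design:** "incorrect dosage (including renal dose adjustment" (the closing bracket follows). It gives no further rule.
- **Section 8.2, Secondary Objectives:** the label and scope are "incorrect dosage (including renal dose adjustment) when the dosage of a component/co-formulation", and the rule then ends "regimen is not correct, i.e. the dosage prescribed does not exist". This is the only operational definition.
- **Section 9.1, Study Design:** the bare label "2. incorrect dosage".
- **Section 9.4, Table 3:** "incorrect dosage [including renal dose adjustment" (the closing bracket follows), without the restriction to non-existent doses.

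The synopsis leaves classification of errors to the investigator, working from clinical records. It also makes two results depend on the classification: the share of hospital episodes with an ART prescribing error, and the percentage of errors. Each is reported overall and by STR versus non-STR.

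**The concern.** The label and the rule in Section 8.2 give different answers for the same order. A dose left unadjusted for renal function is normally a dose that exists, so the label counts it and the rule does not. More generally, any existing dose that is wrong for the patient falls outside the rule.

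The sub-study exists to quantify prescribing errors and to identify those that an STR could avoid. If one of the six types has two incompatible meanings, the counts depend on which one each center follows. The overall proportion is then no longer a measure of a defined quantity, and the cohort comparison carries a classification difference that cannot be separated from a real one. The statistical analysis plan cannot repair this afterwards, because sites enter the classification and fields that were never collected cannot be recovered.

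**Working it through.** The plan gives no figure to reproduce: Section 9.6 states that no formal sample size was determined for the sub-study. The check is a comparison of the passages.

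**Step 1. Is the clause a definition or an example?** It uses *i.e.*, which defines. In the same list, type 1 uses *e.g.* where an example is meant. On its wording the clause is therefore a restriction.

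**Step 2. Apply label and rule to the possible orders.**

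| Order | Label (synopsis, 8.2, Table 3) | Rule in 8.2 |
|---|---|---|
| Dose does not exist, component or co-formulation | error | error |
| Dose exists but is wrong for the patient, for a non-renal reason | error on a plain reading | not an error |
| Existing dose, needed renal adjustment missed | error | not an error |
| Single-strength product ordered at any other strength | error | error, since that strength does not exist |

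Label and rule disagree in rows 2 and 3.

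**Step 3. Does another type catch rows 2 and 3?** Type 1 concerns an absent or incomplete regimen. Type 3 is "incorrect schedule when the schedule mentioned by the physician is not adequate to the regimen prescribed", so its yardstick is the regimen and not the patient's renal function. Type 4 concerns an unavailable pharmaceutical form, type 5 duplication and type 6 contraindicated combinations. None clearly covers them. Section 7.2, by contrast, cites a definition of prescription error that covers any wrong instruction about a normal feature of a prescription.

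**Step 4. Can the recorded data settle it?** Table 3 collects substances, dosage and scheduling, with diagnoses and codes, but no renal function variable. An investigator may see laboratory files (Section 9.5), but the eCRF alone would not show why an order was or was not scored. Section 9.2 recruits centers in four countries.

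**Step 5. What can be said about size and direction?** For cohort S (STR) or N (non-STR), let p be the proportion of episodes with any error when rows 2 and 3 count. Let d be the proportion whose only errors lie in those rows. Under the literal rule:

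- observed proportion = p − d, which is never above p;
- observed difference = (p_S − p_N) − (d_S − d_N);
- observed ratio = (p_S / p_N) × (1 − d_S/p_S) / (1 − d_N/p_N).

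A literal reading can therefore only lower each proportion. The shift in the difference depends on the sign of d_S − d_N, and the shift in the ratio on whether d_S/p_S exceeds d_N/p_N. The protocol gives none of these quantities.

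The nearest figure is in Section 7.2, from one cited study: "the majority of pharmacist interventions (68%) were related to dosage modification". It shows that dosage can be a large class. It does not say how many of those interventions concerned renal adjustment or existing but wrong doses, so it does not estimate d.

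**The case against.** The strongest reply is that this is one loosely worded clause. The renal wording stands in the synopsis, in the Section 8.2 label and in Table 3, which lists what investigators record. Investigators classify from source records with laboratory files available, and Section 9.11.1.1 gives monitors access to those records. Section 9.1 is a short list that also drops the explanations of other types, so it is an abbreviation and not a rival definition.

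Much of this stands. Renal errors can be classified at the site, and it is not settled that they will be left out. What is missing is a consistent instruction and the means to check its use from the eCRF. One could try to reconcile the text by reading the renal label as covering only mistaken adjustments to a non-existent dose, but missed adjustments would then still go uncounted.

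A reader might go further and infer that a fixed-dose STR can hardly score a dosage error, so that the rule favours STR. The documents do not support this. Section 8.2 expressly covers co-formulations. For a product with one strength, any other stated strength does not exist and is scored, whereas a component with several strengths can be ordered at a wrong existing strength and escape. The protocol gives neither product strengths nor renal labelling from which to weigh these effects. Nor does assuming equal uncounted error rates in both cohorts show a bias: the difference is then unchanged, and the ratio moves in favour of STR only if the STR proportion is already assumed to be the lower one.

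**Conclusion.** The concern holds as an internal contradiction in an outcome definition. For existing doses that are wrong for a non-renal reason, exclusion follows from the literal rule. For missed renal adjustment, the protocol says both things. The likely result is undercounting where centers follow the rule and inconsistent scoring where some follow the label.

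The size cannot be derived from the documents, and the direction of any effect on STR versus non-STR cannot be determined. The conclusion rests on reading *i.e.* as defining, and on no other category being clearly intended to hold these errors. It affects one of six error types in a secondary sub-study and leaves the primary adherence endpoint untouched. It should be corrected before classification starts at sites.

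**What to change.** Reconcile the synopsis, Section 8.2, Section 9.1 and Table 3 into one operational definition of error type 2.

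- Remove the restriction to non-existent doses, or turn it into an example. The rule then matches the label and covers existing but incorrect doses and missed renal adjustment, for components and co-formulations alike.
- Have the sponsor name the reference against which investigators assess dosage. This review takes no view on which reference or dose is right.
- Add to Table 3 the renal function data used for that assessment, so that the classification can be checked from the eCRF.

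The cost is a wording change and a few more fields from records already under review. The reported error proportions may rise.

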9.1. Study Design

This is a retrospective non-interventional study that has two outcomes: adherence (the primary focus) and prescription errors (sub-study). While all centers will participate in the Adherence study, only centers where prescription data is available will be included in the Prescription errors sub-study. In order to do so, several research hypotheses were formulated:

that SA accounts for a non-negligible portion of OIA and that both SA and NA are clinically and economically relevant

that STRs, as SA-free regimens, will improve adherence, and generate clinical and economic benefits

that STRs are, by nature, of value in avoiding prescription errors.

According to these research hypotheses, study endpoints were established.

Primary endpoint:

Odds of attaining > 90% adherence in the STR cohort versus non-STR cohort, after adjusting for baseline variables and other confounders, with adherence measured by medication possession ratio based on pharmacy refills.

Secondary endpoints:

Adherence

Average OIA and NA levels, in the STR cohort versus non-STR cohort, after adjusting for baseline variables and other confounders, with adherence measured by medication possession ratio based on pharmacy refills.

Average OIA level, according to the number of pills in the regimen (1, 2-3, 4+), after adjusting for baseline variables and other confounders, with adherence measured by medication possession ratio based on pharmacy refills.

Clinical impact

Odds of becoming unsuppressed (HIV RNA >50 copies /mL in two consecutive measures within regimen duration occurring within the observation period) among subjects who had HIV RNA \leq 50 copies/mL between 1st January 2009 and the start of the regimen (whichever is latest); in STR versus non-STR groups, after adjusting for baseline characteristics and other confounders, using laboratory/monitoring data;

Odds of becoming unsuppressed (defined as above) according to subject adherence level (NA and OIA), after adjusting for baseline characteristics and other confounders, using laboratory/monitoring data;

Odds of becoming unsuppressed (defined as above) with resistance development according to subject adherence (NA and OIA), after adjusting for baseline characteristics and other confounders, using laboratory/monitoring data (n.b. may not be feasible).

Hospitalization

Odds of being hospitalized in STR versus non-STR groups, after adjusting for baseline characteristics and other confounders, using monitoring (hospitalization) data;

Odds of being hospitalized according to subject adherence level (NA and OIA), after adjusting for baseline characteristics and other confounders, using monitoring (hospitalization) data.

Costs

Average monthly ART plus hospitalization costs, adherence (OIA) adjusted, in each STR versus non-STR groups at GDP Purchasing Power Parity (PPP) converted current prices, after adjusting for baseline characteristics and other confounders;

Monthly ART plus hospitalization costs according to subject adherence level (NA and OIA), adherence (OIA) adjusted at GDP PPP converted current prices, after adjusting for baseline characteristics and other confounders.

Ideally, hospitalization and ART costs will be collected at the center level. If not possible, hospitalization costs will be collected from publicly available national lists of DRGs and ART costs from IMS databases of each country.

Prescription errors audit

Number of prescription errors in ART orders in the first 48 hours of hospitalization, overall and according to the cohort. Errors will be classified as:

- 1. absence / incomplete regimen
- 2. incorrect dosage
- 3. incorrect schedule
- 4. incorrect formulation
- 5. duplication of ART therapy
- 6. non-recommended drug-drug combinations (ART-ART and ART-non-ART), as suggested by Yehia et al {27744} and available on the HIV drug interaction website shown in red as contra-indicated; www.hiv-druginteractions.org/Interactions.aspx.

In order to collect this information, all prescriptions made during the first 48 hours of every hospitalization of all patient-regimens included shall be reviewed.

Taking into consideration the endpoints defined, the investigators believe that the study will answer the research questions.

Since this is a retrospective study that will only use data from subjects' clinical files and from prescription / laboratory and pharmacy files, treatment decisions will have already taken place, according to local treatment guidelines and/or routine clinical practice, and will not be influenced by the protocol.

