9.3. Subject Selection

Adherence study

For each included subject, data will be collected for all patient-regimens lasting for at least 90 days during the observation period, that either include Stribild or are EACS v7.0 recommended, once daily regimens containing two NRTI plus one NNRTI or two NRTI plus one PI/r. Two cohorts will be considered: (i) STR and (ii) non-STR (Figure 1).

Figure 1. Study Scheme of Adherence study.

Legend: \bigstar start of patient-regimen; \blacksquare end of patient-regimen; i) STR; ii) non-STR.

STR and non-STR subjects are defined, for administrative purposes, according to the type of regimen they were receiving on 31st December 2013. Note that these STR and non-STR groups of subjects are defined only for subject selection purposes. Once subjects are selected, the

relevant unit of analysis is a patient-regimen and both matching and the statistical analysis will be performed at the patient-regimen level.

A single subject may contribute to the analysis with 1 or more patient-regimens. Moreover, a subject selected as part of the STR group (because he was on STR on 31st December 2013) may contribute in the analysis for both the STR and the non-STR group as the example of subject Z or W, in Figure 1 above.

Data will be collected on patient-regimens that were ongoing between 1st January 2009 and 31st December 2013, this is the observation period, and subjects must have had at least one pharmacy refill in 2013. All patient-regimens must have started before 30th September 2013 to ensure a minimum duration of at least 90 days, as determined in the inclusion criteria. Although patient-regimens may have been started before the beginning of the observation period and may still be in progress at the end of this period, for the purposes of this study, generally only data from the observation period shall be collected. The data collection period is the time during which the centers will enroll eligible subjects and enter the data onto the eCRF.

The patient-regimen selection for the adherence study will involve the following steps, to be initiated as soon as hospital approval has been granted at each site:

- 1. Search in Pharmacy's electronic records the pharmacist will search the pharmacy electronic database in order to identify all patients who have at least one ART refill in 2013.
- 2. Separate these patients into two cohorts according to the regimen they were receiving on December 31st 2013 (STR cohort and non-STR cohort)

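### Hospitalization and loss of suppression are defined as odds per patient-regimen with no allowance for observation time, although a regimen may be observed for 90 days to 5 years

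*Protocol*

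**What the plan says.** Section 9.1 lists the hospitalization endpoints as "Odds of being hospitalized in STR versus non-STR groups, after adjusting for baseline characteristics and other confounders" and "Odds of being hospitalized according to subject adherence level (NA and OIA"). The virological endpoint is "Odds of becoming unsuppressed (HIV RNA >50 copies /mL in two consecutive measures within regimen duration occurring within the observation period"), so its risk window is the regimen's own length.

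Section 9.3 makes the patient-regimen the unit for matching and analysis. It states that "data will be collected for all patient-regimens lasting for at least 90 days during the observation period", and it sets the outer limits: "Data will be collected on patient-regimens that were ongoing between 1st January 2009 and 31st December 2013, this is the observation period". The Synopsis measures regimen duration from first to last refill inside that period, counting from 1 January 2009 for regimens already under way.

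Section 9.8 names a logistic mixed model for binary outcomes, with marginal (GEE) models as an alternative. The Synopsis treats the collected variables as confounders. Table 2 in Section 9.4 holds refill, discontinuation, test and admission dates, but does not list regimen duration as a covariate. The propensity score steps in Section 9.3 do not name it either. Costs, listed just after hospitalization in Section 9.1, are monthly averages.

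Table 2 collects every inpatient episode in the observation period. The hospitalization endpoint does not say whether an admission must fall within the regimen. Section 7.2 defines NA and OIA as proportions of days over the total regimen duration.

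**The concern.** The chance of at least one admission, or of two consecutive raised viral loads, grows with the time watched. An odds per regimen with no time denominator mixes the event rate with the length of observation. If STR and non-STR regimens differ in observed length, the odds ratio partly measures that difference. These endpoints carry the protocol's hypothesis of clinical benefit, so an artefact could be reported as an STR benefit or could hide one.

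Two related gaps add to this:

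- If admissions are counted over all five years, time is equal but admissions are credited to regimens not being taken when they occurred. If they are counted within the regimen, time is unequal. The protocol does not choose.
- NA and OIA run over the whole regimen, so refill gaps after an admission or failure enter the exposure meant to explain that event.

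**Working it through.** The protocol states no figure for these two endpoints (Section 9.6 sizes only the primary adherence endpoint), so there is none to reproduce.

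**Inputs from the protocol**
- Shortest observed regimen: 90 days = 90/365.25 = 0.246 years.
- Longest: 5 years, 1 January 2009 to 31 December 2013. Ratio 5/0.246, about 20.
- 1030 matched pairs of patient-regimens (Section 9.6); two-sided 5% level (Section 9.8).

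**Assumptions (not in the protocol)**
- A constant event rate λ, identical in both cohorts, of 0.05, 0.10 or 0.15 per year.
- Mean observed durations t(STR) and t(non), varied below.

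**Formula.** The risk of at least one event is p = 1 − exp(−λt), so the odds are exp(λt) − 1 and

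OR = [exp(λ·t(STR)) − 1] / [exp(λ·t(non)) − 1].

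Example, λ = 0.10, 1.5 versus 3 years: p = 0.139 and 0.259; odds 0.162 and 0.350; OR = 0.46.

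| STR vs non-STR (years) | λ = 0.05 | λ = 0.10 | λ = 0.15 |
|---|---|---|---|
| 2 vs 2.5 | 0.79 | 0.78 | 0.77 |
| 1.5 vs 3 | 0.48 | 0.46 | 0.44 |
| equal | 1.00 | 1.00 | 1.00 |
| 2.5 vs 2 | 1.27 | 1.28 | 1.30 |
| 3 vs 1.5 | 2.08 | 2.16 | 2.25 |

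The true rate ratio is 1 in every cell.

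**False significance.** With 1030 regimens per cohort and λ = 0.05, a two-proportion test has about a 31% chance of p < 0.05 at 2.5 versus 3 years (OR 0.82). At 2 versus 3 years the chance is about 88% (OR 0.65), and at 3 versus 2 years it is about 88% in the opposite direction (OR 1.54). At equal durations it is 5%.

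**Check of the remedy.** A simulation used durations spread between 90 days and 5 years, rates of 0.02, 0.05 and 0.10 per year, independent cohorts of 1030 and 1500 replicates per scenario. It gave odds ratios close to the formula. On the same data, events per person-time gave rate ratios of 0.98 to 1.01, with rejection in about 3% to 6% of replicates. These are crude contrasts, without matching or covariates.

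**The case against.** The strongest defence is that the protocol leaves room for time. Section 9.8 says the analysis will respect the panel structure, adjustment extends to other confounders, the dates are collected, and an analysis plan not shown here could set the model. That room exists, but none of these passages supplies a time denominator. Panel structure addresses repeated observations, not unequal exposure. The protocol itself fixes the scale as odds, so this is more than detail left for later. Entering duration as an ordinary covariate would be weaker, because it is known only after the regimen starts and may depend on the outcome.

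Other points stand and limit the conclusion:

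- No mean duration, event rate or testing frequency is given by cohort. Equal durations give no bias, and longer STR durations reverse it.
- A reader might infer a built-in bias in favour of STR from the sampling rule: "Within the STR group, priority will be given to non-Atripla patient-regimens so these will be selected first if available". The documents do not support that step. It needs launch or uptake dates they do not contain. Subjects rather than regimens are sampled, Atripla fills any shortfall, and a switch to STR also cuts short the earlier non-STR regimen.
- A reader might also infer that short regimens can hardly show loss of suppression because two tests are required. That rests on an assumed testing interval and on an unknown share of regimens near 90 days.
- The unequal window is explicit only for loss of suppression. For hospitalization the defect in the text is that the window is undefined.

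**Conclusion.** The concern holds as a defect in how two secondary endpoints are defined. Regimens may differ about 20-fold in observed length, and nothing in the protocol accounts for it. Under the assumed equal rates, a modest imbalance of 2 versus 2.5 years moves the odds ratio to 0.79–0.77, and 1.5 versus 3 years moves it to 0.48–0.44. Reversing the imbalance gives 1.27–1.30 and 2.08–2.25. Confidence is high that the time provision is missing. It is not high about the size or direction of any bias in this study, which the documents cannot settle.

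The use of post-event days in NA and OIA follows directly from the Section 7.2 definitions; its size has not been estimated.

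This should be fixed but does not threaten the main result. The primary endpoint is a possession ratio and costs are monthly, so both are already scaled for time.

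**What to change.** - State that admissions count only within the observed regimen duration.
- Analyse hospitalization and loss of suppression as rates (Poisson or negative binomial, log observed time as offset) or as time to first event, censored at the end of the observed regimen. Cluster by subject and report person-years by cohort.
- For the adherence-level analyses, accumulate NA and OIA only up to the event, or to the same elapsed time in event-free regimens.

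The cost is revised endpoint wording and some extra programming. Results become rate or hazard ratios instead of odds ratios. The dates needed are already in Table 2, so eligibility, sampling and data collection do not change.
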